2.2 Secondary Objectives

The secondary objectives will be:

- To compare the overall response rate of KW-0761 versus vorinostat in subjects with relapsed or refractory CTCL;
- To evaluate and compare improvements in QoL measurements, Skindex-29, FACT-G and EQ-5D-3L for subjects receiving KW-0761 versus vorinostat;
- To evaluate and compare improvements in the Pruritus Evaluation (Likert scale & Itchy QoL) for subjects receiving KW-0761 versus vorinostat;
- To estimate the duration of response for both the KW-0761 and vorinostat arms for those subjects with relapsed or refractory CTCL responding to treatment;
- To determine if subjects who relapse on vorinostat can achieve response upon cross over to treatment with KW-0761;
- To further assess the safety of KW-0761;
- To describe the immunogenicity of KW-0761.

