3.4 Eligibility for Cross-over to KW-0761

Subjects who are randomized to the vorinostat arm may cross over to KW-0761 upon progression or in the event of intolerable toxicity (see Section 5.3). Crossover may take place following discussion with the Medical Monitor or designee and receipt of approval for cross over from Kyowa Kirin Pharmaceutical Development, Inc. (KKD). However, they must

continue to fulfill inclusion criteria 6 through 15, and will be excluded if they fulfill the exclusion criteria, except for exclusion criteria 1, 12 and 13 (refer to Section 3.3).

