5.3 Cross-over to Study Drug KW-0761

Subjects who have received 2 full treatment cycles and demonstrate progression of disease on treatment with vorinostat at the 8 week (Cycle 2, Day 26-28) assessment, or anytime thereafter, may cross over to treatment with KW-0761 after discussion with Medical Monitor or designee and receipt of approval for cross over from KKD. Investigators should strive to maintain subjects on treatment for at least the 8 week period, adjusting the dose of vorinostat as needed for toxicities in order to allow sufficient time to see effect. In cases where a subject's disease progresses rapidly (i.e., prior to 8 weeks), the Medical Monitor or designee should be contacted and may consider the possibility of early crossover, if appropriate for that subject. All subjects must undergo the full extent of disease evaluations (including CT scanning) to document PD prior to crossover.

There must be at least 2 weeks between the last dose of vorinostat and first dose of KW-0761. Subject must continue to meet eligibility criteria outlined in Section 3.4 and all toxicity must have resolved to Grade \leq 1 or to baseline in order to receive KW-0761. Treatment with KW-0761 should commence with procedures outlined for Day 1 in Table 1 of Study

Procedures for the first treatment cycle. In cases where a subject's disease progresses rapidly, the Medical Monitor or designee should be contacted and may consider initiation of treatment with KW-0761 prior to the 2-week washout period.

For subjects who are unable to tolerate the toxicities associated with vorinostat treatment, dose reduction should be initiated in an attempt to have the subject complete 2 full cycles of treatment. If the subject is unable to tolerate treatment with vorinostat despite attempts at dose reduction and has not had documented disease progression, the subject may receive KW-0761 after consultation with the Medical Monitor or designee and subsequent approval documentation from the Sponsor.

Drug intolerance is defined as:

- A serious AE attributed to the drug;
- \geq Grade 3 AEs excluding inadequately treated nausea, vomiting and diarrhea and alopecia.

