7.2 Efficacy Evaluations

Response in skin and blood will be evaluated every 4 weeks during treatment. In the first year of treatment, response in lymph nodes and viscera will be documented at 4 weeks after the start of study treatment (end of Cycle 1) and every 8 weeks thereafter. After the first year, response in the lymph nodes and viscera will be documented every 16 weeks. In the first year of treatment, the global composite response (including skin, blood, lymph nodes and viscera) will be assessed at 4 weeks (end of Cycle 1) and every 8 weeks thereafter (Cycle 3, 5, etc.); after the first year, global composite response will be assessed every 16 weeks (Cycle 17, 21, etc.).

For those subjects who cross over from the vorinostat arm to KW-0761 treatment, response within the second arm of the study will be measured from the first day of dosing with KW-0761. Baseline measurements for this arm are considered to be those taken at the last assessment which documented progression on vorinostat or if repeated, assessment completed closest to and before the first KW-0761 infusion (i.e., mSWAT done on Cycle 1, Day 1 is the new baseline).

Prior to starting study treatment, visual inspection of the skin with photographs and measurements (mSWAT), assessment of CT images and hematological examinations will be done to document extent of disease. Skin disease will be evaluated using a modification of the SWAT (Olsen, 2007; Stevens, 2002). Response for skin will be based on mSWAT scores. In addition, pruritus will be evaluated using a Likert scale and Itchy QoL. Lymph nodes and visceral disease will be evaluated by CT. The response in blood will be assessed by flow cytometry.

The response in all compartments (skin, blood, lymph nodes and viscera, as applicable) and overall response will be assessed, except as otherwise noted, in accordance with the response criteria determined by consensus of the International Society of Cutaneous Lymphomas (ISCL), the United States Cutaneous Lymphoma Consortium (USCLC) and the Cutaneous Lymphoma Task Force of the European Organization for Research and Treatment of Cancer (EORTC) (Olsen, 2011).

If clinical progression is noted at any time prior to the scheduled assessments for efficacy, the assessments (CT, mSWAT, skin photographs and flow cytometry) should be done at that time to fully document disease progression. CT must be performed even if previously negative at baseline.

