For the Pruritus Evaluation Likert Scale data, the changes in the Likert Scale score from baseline at different timepoints up to the cycle 11 assessments during the randomized treatment period will be analyzed using Wilcoxon rank sum test. The treatment difference in the median change of the Likert Scale score from baseline will be estimated using the Hodges-Lehmann estimate and a two-sided 95% confidence interval for the treatment difference will be obtained using the method of Moses.

All quality of life measurements and changes from baseline will be summarized descriptively at each scheduled time point.

For subjects who cross over from the vorinostat arm to the KW-0761 arm, ORR during the crossover portion of the trial will be estimated in a similar fashion as described above for ORR of the randomized therapy. In addition, the quality of life assessments during the crossover portion will be measured at the end of the first cycle after the first day of dosing for KW-0761. Baseline measurements for the crossover portion are considered to be those taken at the last assessment point of the previous cycle. The quality of life measurements as well as the changes from baseline during the crossover portion of the trial will be summarized descriptively. All summaries for the crossover portion will be purely descriptive. No statistical comparisons will be made for data collected during the crossover portion.

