Listing 16.2.8.26	Saliva Sample for Genetic Analysis – KW-0761 Treatment Only
Listing 16.2.8.27	Anti-KW-0761 Antibody Response
Listing 16.2.8.28	Anti-KW-0761 Antibody Response for Subjects with Infusion Reactions
Listing 16.2.8.29	CCR4 Expression
Listing 16.2.8.30	General Comments

Table 14.1.1.1
Subject Disposition
Intent-to-Treat Set

	Vorinostat n (%)	KW-0761 n (%)	Total n (%)
Subjects Randomized	xx (100.0)	xx (100.0)	xx (100.0)
Subjects Randomized and Did Not Receive Any Assigned Study Drug	xx (xx.x)	xx (xx.x)	xx (xx.x)
Subjects Randomized and Treated	xx (xx.x)	xx (xx.x)	xx (xx.x)
Subjects Discontinued Randomized Study Drug	xx (xx.x)	xx (xx.x)	xx (xx.x)
Study termination by sponsor	xx (xx.x)	xx (xx.x)	xx (xx.x)
Progressive disease per CTCL response criteria	xx (xx.x)	xx (xx.x)	xx (xx.x)
Progressive disease - Clinical	xx (xx.x)	xx (xx.x)	xx (xx.x)
Pregnancy	xx (xx.x)	xx (xx.x)	xx (xx.x)
Withdrawal of consent	xx (xx.x)	xx (xx.x)	xx (xx.x)
Subject requires prohibited concomitant medication	xx (xx.x)	xx (xx.x)	xx (xx.x)
Protocol noncompliance	xx (xx.x)	xx (xx.x)	xx (xx.x)
Investigator decision	xx (xx.x)	xx (xx.x)	xx (xx.x)
Adverse event	xx (xx.x)	xx (xx.x)	xx (xx.x)
Death	xx (xx.x)	xx (xx.x)	xx (xx.x)
Other	xx (xx.x)	xx (xx.x)	xx (xx.x)
Subjects Randomized to Vorinostat and Crossed Over to KW-0761	xx (xx.x)	-	xx (xx.x)
Subjects Discontinued from the Study	xx (xx.x)	xx (xx.x)	xx (xx.x)
Study termination by sponsor	xx (xx.x)	xx (xx.x)	xx (xx.x)
Withdrawal of consent	xx (xx.x)	xx (xx.x)	xx (xx.x)
Death	xx (xx.x)	xx (xx.x)	xx (xx.x)
Lost to Follow-up	xx (xx.x)	xx (xx.x)	xx (xx.x)
Subject did not meet Inc./Exc. criteria	xx (xx.x)	xx (xx.x)	xx (xx.x)
Other	xx (xx.x)	xx (xx.x)	xx (xx.x)
Analysis Set			
Intent-to-Treat Set	xx (xx.x)	xx (xx.x)	xx (xx.x)
Safety Analysis Set	xx (xx.x)	xx (xx.x)	xx (xx.x)
Efficacy Evaluable Set	xx (xx.x)	xx (xx.x)	xx (xx.x)

Note: Percentage is calculated using the number of randomized subjects as the denominator.

Table 14.1.1.2
 Subject Disposition - Crossover Portion
 Subjects Who Are Randomized to Vorinostat and Crossed Over to KW-0761

	Total n (%)
Subjects randomized to Vorinostat and crossed over to KW-0761	xx (100.0)
Due to Progression	xx (xx.x)
Due to Intolerance	xx (xx.x)
Subjects who crossed over to KW-0761 but did not receive KW-0761	xx (xx.x)
Subjects who crossed over to KW-0761 and received KW-0761	xx (xx.x)
Subjects crossed over to KW-0761 and discontinued KW-0761	xx (xx.x)
Study termination by sponsor	xx (xx.x)

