By Investigator's Assessment		
Time to Response (months)*		
n	xx	xx
Mean	xx.x	xx.x
Std Dev	xx.xx	xx.xx
Median	xx.x	xx.x
Minimum	xx	xx
Maximum	xx	xx
By Independent Review Committee		
Time to Response (months)*		
n	xx	xx
Mean	xx.x	xx.x
Std Dev	xx.xx	xx.xx
Median	xx.x	xx.x
Minimum	xx	xx
Maximum	xx	xx

* For subjects with confirmed complete response or partial response.

Table 14.2.2.7.2
 Summary of Time to Response During Randomized Treatment Period by Disease Type
 Intent-to-Treat Set

Disease Type = MF		Vorinostat N=xxx	KW-0761 N=xxx
By Investigator's Assessment			
Time to Response (months)*			
n		xx	xx
Mean		xx.x	xx.x
	Std Dev	xx.xx	xx.xx
Median		xx.x	xx.x
Minimum		xx	xx
Maximum		xx	xx
By Independent Review Committee			
Time to Response (months)*			
n		xx	xx
Mean		xx.x	xx.x
Std Dev		xx.xx	xx.xx
Median		xx.x	xx.x
Minimum		xx	xx
Maximum		xx	xx

* For subjects with confirmed complete response or partial response.

<<Programming Note: Repeat for the following subgroup: Histologically Confirmed Diagnosis (SS).>>

The following tables will have a similar layout as Table 14.2.2.7.1 and 14.2.2.7.2:

Table 14.2.2.7.3
Summary of Time to Response During Randomized Treatment Period
Efficacy Evaluable Set

Table 14.2.2.7.4
Summary of Time to Response During Randomized Treatment Period by Disease Type
Efficacy Evaluable Set

Table 14.2.2.8.1
 Summary of Best Overall Response Based on Investigator's Assessment During Crossover Portion
 Intent-to-Treat Set
 Subjects Who Are Randomized to Vorinostat and Crossed Over to KW-0761

	Total (N=xx)
	n (%)
Overall response (confirmed CR + PR)	xx (xx.x)
95% CI*	(xx.x, xx.x)
Best Overall Response	
Complete response (CR)	xx (xx.x)
Confirmed CR	xx (xx.x)
Partial response (PR)	xx (xx.x)
Confirmed PR	xx (xx.x)
Stable disease	xx (xx.x)
Progressive disease	xx (xx.x)
Not Assessable	xx (xx.x)

Note: Percentage is calculated using the number of subjects in the column heading as the denominator.
 * 95% CI for response rate is the exact 95% confidence interval.

Table 14.2.2.8.2
 Summary of Best Overall Response Based on Investigator's Assessment During Crossover Portion
 By Disease Type
 Intent-to-Treat Set
 Subjects Who Are Randomized to Vorinostat and Crossed Over to KW-0761

Disease Type = MF

	Total (N=xx)
	n (%)
Overall response (confirmed CR + PR)	xx (xx.x)
95% CI*	(xx.x, xx.x)
Best Overall Response	
Complete response (CR)	xx (xx.x)
Confirmed CR	xx (xx.x)
Partial response (PR)	xx (xx.x)
Confirmed PR	xx (xx.x)
Stable disease	xx (xx.x)

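### The crossover objective concerns subjects who relapse on vorinostat, but every planned crossover response rate pools them with subjects who switched for intolerance without documented progression

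*SAP*

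**What the plan says.** Protocol 2.2 and SAP 2.2 list the same secondary objective: "To determine if subjects who relapse on vorinostat can achieve response upon cross over to treatment with KW-0761".

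Protocol 3.4 says that subjects randomized to vorinostat "may cross over to KW-0761 upon progression or in the event of intolerable toxicity". Protocol 5.3 sets out the second route: a subject who cannot tolerate vorinostat despite attempts at dose reduction and who "has not had documented disease progression, the subject may receive KW-0761 after consultation with the Medical Monitor or designee", with later sponsor approval. SAP 3.2.2.4 repeats this.

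For the analysis, SAP 6.11.2.4 takes all subjects who cross over and says that "ORR during the crossover portion of the trial will be estimated in a similar fashion" as for randomized therapy. It makes all crossover summaries descriptive and rules out statistical comparisons. The shells for Tables 14.2.2.8.1 and 14.2.2.8.2 each have one Total column, whose N is the denominator. The second repeats the first by disease type. Tables 14.2.2.8.3 and 14.2.2.8.4 copy both layouts for the Efficacy Evaluable Set.

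The reason for crossover is collected. Table 14.1.1.2 counts progression and "Due to Intolerance" on separate rows, and Listing 16.2.1.2 shows the reason for each subject.

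**The concern.** The objective is about one group and the planned estimate is about a wider one. A subject who switches for progression has met the PD criteria on vorinostat. A subject who switches for intolerance under Protocol 5.3 has no documented progression and may be in stable disease or partial response. The two groups start KW-0761 from different disease states, so there is no reason to expect equal response rates.

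At stake is how the figure will be read. Because it is the only product of this objective, the crossover ORR is likely to be cited as the activity of KW-0761 after vorinostat has failed. As planned, it includes an unstated share of subjects in whom vorinostat was stopped for another reason.

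**Working it through.** The documents state no sample size, assumed rate or precision target for the crossover ORR, so there is no plan figure to reproduce. The check has two parts: a comparison of the texts, then an illustration of size.

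**1. Population named against population analysed**

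| Element | Place | Who is included |
|---|---|---|
| Objective | Protocol 2.2, SAP 2.2 | Subjects who relapse on vorinostat |
| Eligibility to cross over | Protocol 3.4 and 5.3, SAP 3.2.2.4 | Progression, or intolerance without documented progression |
| Crossover ORR | SAP 6.11.2.4 | All who cross over |
| Response tables | 14.2.2.8.1 to 14.2.2.8.4 | All who cross over, split only by disease type |
| Planned subgroup analyses | SAP 6.11.2.7 | PFS on first assigned therapy only |
| Optional subset factors | Protocol 10.3 | Reason for crossover not named |
| Reason for crossover | Table 14.1.1.2, Listing 16.2.1.2 | Recorded, but not applied to response |

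No row gives a response estimate confined to the first row's population.

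**2. Size of the difference**

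Let q be the share of crossover subjects who switched for intolerance.

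- Pooled ORR = (1 - q) × ORR_prog + q × ORR_intol
- Pooled ORR - ORR_prog = q × (ORR_intol - ORR_prog)

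The difference is zero only if q = 0 or the two rates are equal. All inputs below are assumptions. With ORR_prog = 20%:

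| q | Pooled, ORR_intol = 40% | Shift (points) | Pooled, ORR_intol = 10% | Shift (points) |
|---|---|---|---|---|
| 10% | 22% | +2 | 19% | -1 |
| 20% | 24% | +4 | 18% | -2 |
| 30% | 26% | +6 | 17% | -3 |
| 40% | 28% | +8 | 16% | -4 |

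Wider assumptions widen the range. At q = 40%, rates of 20% and 50% give 0.40 × (50 - 20) = +12 points, and rates of 30% and 10% give 0.40 × (10 - 30) = -8 points.

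**3. Effect on precision**

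Take 100 crossover subjects, q = 20%, and rates of 20% and 40%. Responders number 16 of 80 progressors and 8 of 20 intolerant subjects.

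- Pooled: 24/100 = 24%, exact 95% CI 16.0% to 33.6%
- Progressors only: 16/80 = 20%, exact 95% CI 11.9% to 30.4%

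The interval widens from 17.6 to 18.5 points, and the estimate then refers to the group in the objective.

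**The case against.** The strongest reply is that this is a matter of presentation in a descriptive summary that is not a key secondary endpoint. The objective asks whether such subjects can respond and sets no threshold or precision target. The table titles claim only to describe subjects who crossed over, Table 14.1.1.2 shows the mix of reasons, and Listings 16.2.1.2 and 16.2.6.20 together identify every responder among the progressors. SAP Section 1 also allows supplementary analyses in the study report. Because Protocol 5.3 tells sites to try dose reduction first, the intolerance group may be small. In the example above, the 4-point shift lies well inside the progressors' own confidence interval.

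Most of this stands, and it limits the weight of the point. It does not remove it. A listing that a reader must join by hand is not a planned estimate, and an analysis added later was not specified in advance.

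Two stronger readings are tempting, but the documents do not support them.

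- *That intolerant subjects have no valid baseline.* Protocol 7.2 and SAP 5.1 first describe the crossover baseline as measurements "taken at the last assessment which documented progression on vorinostat", which such a subject lacks. The same sentence goes on to allow a repeat assessment closest to and before the first KW-0761 infusion. SAP 6.2 sets the general rule that crossover baseline is the last measurement before the first KW-0761 dose. A baseline is therefore defined.
- *That carried-over vorinostat effect will be credited to KW-0761.* Protocol 5.3 requires at least 2 weeks between the last vorinostat dose and the first KW-0761 dose. Its stated exception is rapid progression, not intolerance. Carry-over is not excluded, but nothing in the documents shows it.

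**Conclusion.** The population mismatch holds on the text alone. The objective concerns subjects who relapse on vorinostat, and all four planned crossover response tables pool both reasons for crossover.

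The size of the discrepancy cannot be determined from the documents. The range of -4 to +8 points rests entirely on assumed rates and shares, and the direction is unknown. If few subjects switch for intolerance, the effect is small. Power, type I error and the primary PFS result are not affected.

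The objective also has a wording problem. Protocol Table 7.2.4-1 and SAP Table 5.1-1 define Relapse as recurrence of disease after a CR. Read literally, the objective would cover only subjects who had a complete response on vorinostat and lost it. This point takes progression on vorinostat to be what is meant, and the plan should say so.

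**What to change.** - In SAP 6.11.2.4, name as the analysis for this objective the confirmed ORR, with exact 95% CI, in subjects who crossed over for documented progression and received KW-0761.
- In Tables 14.2.2.8.1 to 14.2.2.8.4, replace the single column with three: *Crossed over for progression*, *Crossed over for intolerance* and *Total*. Take the reason from the data already used for Table 14.1.1.2 and Listing 16.2.1.2. Base any statement about response after vorinostat failure on the first column.
- State in SAP 2.2 or 6.11.2.4 that relapse in this objective means progression on vorinostat, not the table definition of recurrence after CR.

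The cost is two extra columns from an existing variable and a wider confidence interval in the smaller, relevant subset. No data collection or treatment rule changes.

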6.11.2.5 Analyses of Exploratory Efficacy Variables

Although not considered a secondary endpoint, a comparison between treatment arms for OS and TTF will be conducted using the same method as described above for the analysis of PFS based on the ITT set and will be considered exploratory.

Additional exploratory analysis will be performed for comparison of PFS between subjects with any exposure to KW-0761 versus subjects with vorinostat only. For this analysis, the PFS for subjects who cross over from the vorinostat arm to KW-0761 will be calculated from the first dose of KW-0761.

Statistical analyses on OS using follow-up data may take place after database lock for the study and will be reported as supplemental to the Clinical Study Report.

The following exploratory analyses will be performed for OS to account for crossover effect:

- The rank-preserving structural failure time (RPSFT) model will be applied to allow a direct comparison of the randomized treatment groups by adjusting the OS of subjects who crossed over so that it reflects the OS had they not received KW-0761.¹²
- The Inverse Probability of Censoring Weighting (IPCW) model will also be applied. In this method subjects who cross over from IC to KW-0761 will be censored and subjects remaining on IC will be weighted to compensate for missing data. The bias introduced by the crossover will be corrected by weighting each subject by the inverse of the predicted probability of not being censored at a given time.¹²

